## 4.2 Study Outcome Measures (See Table 1)

### 4.2.1 Primary Outcome Measures

#### Objective 1: To identify the most effective strategy to deliver FN

**Our primary outcome measure is receipt of behavioral health services within 90 days (yes/no)** will be defined as first encounter with behavioral health services within 90 days of randomization obtained from the electronic health record including Family Partner's template documentation.

Related to this primary objective, we will evaluate *time-to-receipt of behavioral health services* defined as time from randomization to first behavioral health service encounter obtained from the electronic health record, including family partner's template documentation. Dates will be obtained from administrative and billing data (electronic health records) for services within DotHouse, and FP documentation for services outside the health center.

A second primary outcome includes change in child symptoms over time.

- Pediatric Symptom Checklist-17 (PSC-17). A 17-item psychosocial screen designed to recognize cognitive, emotional, and behavioral problems. Three subscale Internalizing, Attention, and Externalizing have specific cutoffs and provide additional guidance regarding need for further follow-up. PSC-17 is embedded in the Epic (electronic health record) as a self-scoring form. It is widely used and has been validated in diverse populations.
- The Survey of Wellbeing of Young Children (SWYC). The SWYC screens for cognitive, motor, language, and social-emotional development among children up to 5½ years of age. We will track behavioral symptoms using the SWYC's Preschool Pediatric Symptom Checklist (PPSC), an 18-item questionnaire that has demonstrated strong concurrent validity with the Child Behavior Checklist (CBCL) and parents' reports of socio-emotional diagnoses as well as acceptability in diverse populations. Translations are available in a range of languages and the SWYC is currently being incorporated into the Epic system used at DotHouse.

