- Support for Access to Behavioral Health Services. The FP will work with the family after referral from the pediatric clinician to access recommended services, support family preferences, and engagement in treatment through the creation of a Family Plan. FPs will employ problem solving strategies to assist families to resolve logistical barriers, MI to address hesitancy to engage in services, and provide care coordination including with schools and other providers.
- Engagement in evidence-based treatment. FN aims to support family adherence to the recommendation for further behavioral healthcare. The FP, who is trained in motivational interviewing and collaborative decision making, will use these skills to explore parental response to any identified concerns, with the goal of supporting parental engagement in the referral process and behavioral health treatment plan.
- Monitoring to achieve family goals. Active FN will continue until the goals articulated in the Family Plan have been achieved, at which point the FP will be available on as needed basis for up to 12 months.
- Family strengthening. FNs will refer families to local support groups and parent mental health services if needed.
- Connection to concrete resources: FPs, who will receive extensive training on available local resources and entitlements, will connect families to community-based resources (e.g., disability insurance, utility discounts).

We will test 4 FN delivery components in a highly efficient experimental design. Families will be randomized to one of eight combinations of components that will be delivered by FPs. The following is a description of the specific components.

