**Because some families will be referred for a behavioral health visit without referral to a FP, but may in fact benefit from a visit with an FP based on assessment by the behavioral health clinician, we will allow for the behavioral health provider at DotHouse to refer to the study. This provider will also be able to follow either Pathway 1 or Pathway 2 as described above. Any member of the child's care team may refer to the FP**

**Initial contact with FP.** As much as feasible, the FP will meet with the child and family during the visit. If the FP is not available (e.g. evening/weekend visits,) the initial contact will be via telephone. During this visit/contact, the FP will describe this research study, including randomization to different study conditions, and obtain consent. The FP will obtain written consent and HIPAA authorization for all in-person meeting. The FP will obtain verbal consent for both study participation and HIPAA authorization when the initial contact is by telephone. (See INSPIR for further detailed description of recruitment, consenting, and randomization procedures.)

Families who decline participation in the study will have the option to work with health center care managers (instead of the study FPs) who also offer care coordination. Those families will not be randomized or followed as part of the study.

If during the discussion with the FP, the parent states that s/he is interested in the study but not interested in seeking behavioral services at this time, the FP will ask the parent if she can reach out to them in ~ 3 months to see if services for the child are desired at a later date. If upon recontacting the

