family, they would like services and would like to work with the FP, the family will have the opportunity to enroll in the study and be randomized to a study condition. This group of parents will be called the “watchful waiting” group. The watchful waiting group will NOT be consented at the time of initial contact. If they are interested in pursuing services for their child at the time of recontact, the parent and child will be offered study participation at that time and will have the opportunity to consent to or decline participation. We have included this group based on our clinical experience. We find that many families wish to delay services for a number of reasons including life events (family moving, expecting a new baby) and timing (child going away for the summer, want services through school and school ending or not in session). We would like to make study participation available for such families.

The FP will administer the baseline assessment measures and then the family will be randomized (on an individual basis through a randomization generator centralized with the study statistician) to a study condition. If the family declines participation, the FP will refer the family to health center care managers and have no further contact with the family.

**Randomization Procedures.** Before initiation of FN, FPs will assign each family an experimental condition using a computer program. The computer program will use both a randomly-generated number and “minimization procedures” to minimize imbalances across conditions with respect to target variables, including family/child characteristics (e.g., education, gender, race/ethnicity, screening score). In this procedure, the first participant is assigned at random. Subsequent participants have a p chance of being randomly assigned and a 1-p chance of being automatically assigned to the condition that would most reduce imbalance based on selected sample characteristics. Minimization procedures are considered best practices for sequential assignment. Families with more than one child enrolled will participate in the same random condition for all children.

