**Development of a service plan.** In consultation with the primary care team and the pediatric integrated behavioral health clinician, the family partner will work with the family to collaboratively choose from a selection of referral options: onsite integrated behavioral health services with a clinician embedded in primary care pediatrics; onsite behavioral health services provided in the behavioral health department; school based services; and/or referral to an external behavioral health clinician or agency.

**Ensuring linkage with service.** The family will receive assistance with referral and coordination of care based on the child’s needs and the family’s interest. The FP will ensure that a referral is made, an appointment scheduled, support family engagement in services through such activities as text reminders and assistance with transportation.

**Ongoing engagement with FP.** Families’ ongoing engagement with the FP will be guided by the core components of FN described above, family needs, and the study condition to which they were assigned. For example, some families will meet with the FP in the community, others will only do so by phone or in the clinic; some may use Act.MD to assist with care coordination with school or conduct remote visits, others will not have access to this technology. Based on our previous experience, we expect considerable variation in the intensity of engagement among families. The FP will have a manualized intervention workbook that will help guide their interaction with families. The FP will document all FN activities and contacts in a FN log within the EHR. We expect that the range of ongoing activities might include assistance in obtain school evaluations and necessary accommodations (504B plan, IEP); linkage to community-based supports such as parent groups and recreational activities; trouble shooting challenges to accessing services; and coordinating services between primary care, school, and specialty services. The Family Partner will also complete a Family Needs worksheet that will be used to summarize the amount of support required by a family. This worksheet will not be administered to participants but may be used as process data by the research team.

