## 11.2 Source Documents

This study includes data collection and management tools that also meet HIPAA security rules to protect confidentiality and security of protected health information.

**Electronic Health Record (EHR):** Data will be abstracted from the EHR of children including diagnoses (from the child's problem list), basic demographic data, and information on scheduled appointments, missed appointments, screening tools administered, screening results, referrals made, referrals completed, billing codes, and surveys collected through MyChart, the EHR's patient portal. MyChart is an interactive system integrated into the patient EHR (Epic/ OCHIN) and offers patients personalized and secure on-line access to portions of their medical records and also allows providers to send messages and to communicate with patients. MyChart will be used to communicate with families, conduct screening, and monitor symptoms, and track study outcomes / measures. Epic/OCHIN is a fully encrypted, HIPAA compliant system. EHR records at the health center are further protected by firewall

technology. The study investigators will only receive de-identified, ID coded MyChart collected data from DotHouse.

All data will be provided by DotHouse to the study investigators in ID coded form.

FP visit templates: FPs will document in the EHR the details of the eight tasks outlined in protocol manuals: 1) initial encounter, 2) assessment of barriers, 3) plan to address barriers, 4) referrals to service (type and location) 5) confirming appointments scheduled, 6) confirming appointments attended, 7) post-assessment follow-up, and 8) connecting with treatment services. De-identified logs will be scored by study staff to measure the number and nature of completed tasks by the FP.

BACO billing data: We will triangulate BACO billing data with EHR data documenting service use. BACO data will allow us to capture behavioral health services provided outside of DotHouse. BACO billing data will be de-identified by staff at DotHouse who are responsible for maintaining the cross walk between patient name and study ID.

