### **12.2 Sample Size Determination**

#### **Sample Size and Power.**

Of the three measures to operationalize engagement, we powered our study on the dichotomous variable “receipt of BH services within 90 days” - the most conservative estimate. We base our power calculation on the number needed to detect the smallest differences in primary outcomes that are of clinical importance. Our formative work with staff at DotHouse and other community health centers indicates that a relative risk of approximately 25% would be considered clinically significant. Therefore, if 60% of families in the core navigation condition engage in mental health services (estimates based on our prior work), to detect a 25% difference (i.e. 75% of families in any of the FN delivery conditions engage in services), and assuming 2-tailed tests and a type 1 error rate of 5%, approximately 304 participants are required to detect this effect (n=38 in each of 8 cells). Although 304 participants are required for our power analysis, we will be enrolling 715 human subjects which include 304 parent/legal guardian, 304 index children for primary analysis and around 107 siblings for families with more than one eligible child. Additional sibling analysis will be done to explore differences in service goals etc.

We expect strong effects of study mediators, in particular fidelity variables and variables that are central to our theoretical model, such as increased parent capacity. Following published guidance based on an empirical review, we estimate that our design will have at least 80% power to detect mediation effects where the paths from independent variable to mediator and from mediator to outcome are of at least small-to-medium effect (ES=.26). Given that our mediation analyses are designed to support decisions regarding intermediate outcomes to be tracked for quality control and assurance, effect sizes less than this magnitude are not considered to be clinically important. In contrast, analyses of patient-level treatment moderators are exploratory as we have no evidence to support hypotheses of any effect.

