**Objective 1: Effectiveness of FN delivery strategies.**

Following an intent-to-treat model, multiple regression models will be used to test hypotheses regarding the main effects of the three delivery strategies and their combined effects on the study's primary outcome, engagement in appropriate mental health services. A series of increasingly complex models will be constructed to address each specific index of outcome. For example, a logistic regression analysis will test receipt of behavioral health services within 90 days. Cox regression (proportional hazards) analyses will then be used to test the effect of each factor on time-to-scheduling date, and then on time-to-receipt of behavioral health services (with *time to third-next-available appointment* included as a covariate). Given that children may be referred to behavioral health services beyond those designated as primary in their initial visit, multi-level models will then be constructed with time-to-receipt of each behavioral health service as an outcome and with services clustered within child. Similarly, engagement in services will first be analyzed with logistic regression using our definition of engagement in care as a binary outcome, with subsequent multilevel models to analyze engagement in multiple services.

For outcomes involving engagement with services, sensitivity analyses will be conducted in which missing data from the EHR is interpreted as failure to engage in services. While we do not hypothesize interactions among the delivery strategies, these will also be explored. Following recommendations for factorial designs, effect coding (not dummy coding) will be used for experimental conditions to assess for interaction. In addition to evaluating effects "at the margins" using all available cells, results for each individual cell will also be reported, as will simple main effects.

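### Families can be randomised at different steps toward a first behavioral health encounter, and the 90-day model names no covariate for that state, so a modest precision gain goes unused

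*Combined protocol and SAP*

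**What the plan says.** The powered outcome (section 4.2.1) is a "first encounter with behavioral health services within 90 days of randomization".

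The protocol describes more than one state at that time zero:

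- Section 8, on support for access, describes work once a referral exists: "The FP will work with the family after referral from the pediatric clinician to access recommended services".
- Section 9, on referral to the FP, notes that "some families will be referred for a behavioral health visit without referral to a FP". It lets the behavioral health provider, having assessed such a child, send the family to the study.
- Section 9, on linkage, lists among the procedures after randomisation: "The FP will ensure that a referral is made, an appointment scheduled".
- Section 7.2 excludes children actively engaged in the service concerned. It does not exclude a child who has only a referral or a booking.

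The information is collected. Section 11.2 has the EHR extract include "information on scheduled appointments, missed appointments, screening tools administered, screening results, referrals made, referrals completed, billing codes".

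The plan does not name it as a design or analysis variable. The minimisation variables in section 9 are given as "including family/child characteristics (e.g., education, gender, race/ethnicity, screening score"). Section 12.3 lists baseline characteristics to compare, a logistic model for the 90-day outcome and a set of moderators, and referral or appointment state appears in none of them. The only covariate named is time to third-next-available appointment, which measures appointment supply and belongs to the Cox analyses. Section 12.3 also plans to "test the effect of each factor on time-to-scheduling date", without saying from when that time runs.

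**The concern.** A child who already has a referral or a booked visit is likely to be closer to a first encounter than one whose family has yet to choose a service. If so, state at randomisation predicts the 90-day outcome. Leaving out a strong predictor that is already collected gives up precision on all four main effects, and each of those estimates feeds the choice of components for the optimised model. It also leaves each estimate exposed to chance imbalance in that state.

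The scheduling analysis raises a narrower question of definition. If any child holds an appointment made before randomisation, time to scheduling measured from randomisation is zero or negative. The plan gives no rule for that case.

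**Working it through.** **The plan's own figure.** Section 12.2 gives 60% v 75%, "assuming 2-tailed tests and a type 1 error rate of 5" per cent, and 304 families. It states no power for this test, so 80% is assumed because it reproduces 304. Each two-level factor compares half the families with half, 152 v 152.

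n per level = [1.960·√(2·0.675·0.325) + 0.8416·√(0.60·0.40 + 0.75·0.25)]² / 0.15² = (1.298 + 0.550)² / 0.0225 = 151.9, so 152 per level and 304 in total. Power at 152 v 152 is 80.0%. The calculation is unadjusted and takes no credit for covariates.

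**Adding entry state.** The documents give neither input, so both are assumptions: q, the share already advanced at randomisation (20-50%), and the gap in 90-day rate between advanced and early children at the control level (10-40 points). For simplicity there are two states and a common odds ratio within state, with marginal rates held at 60% and 75%. In each stratum, m is the number per level, c and t are the control and treated rates, and p̄ is their mean. The state-stratified (Mantel-Haenszel) test then uses:

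- numerator = Σ m(t − c)/2
- null variance V0 = Σ m·p̄(1 − p̄)/2
- alternative variance V1 = Σ m[c(1 − c) + t(1 − t)]/4
- power = Φ[(numerator − 1.960·√V0)/√V1]

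Worked case, q = 30% and gap 30 points:

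- Advanced children (m = 45.6): 81.0% v 89.9%. Early children (m = 106.4): 51.0% v 68.6%. Odds ratio 2.10 within state.
- Numerator = 152·0.15/2 = 11.4; V0 = 15.62; V1 = 15.17.
- Power = Φ[(11.4 − 1.960·3.953)/3.894] = Φ(0.94) = 82.6%.
- Without strata, V0 = 16.67 and V1 = 16.25, giving Φ(0.84) = 80.0%.

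| Gap (points) | Adjusted power at 304, q = 20-50% | Families needed for 80% |
|---|---|---|
| 0 | 80.0% | 304 |
| 10 | 80.3-80.4% | 301-302 |
| 20 | 80.9-81.5% | 293-297 |
| 30 | 81.9-83.3% | 279-289 |
| 40 | 83.3-85.7% | 261-279 |

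**Simulation check.** Logistic regression with four effect-coded factors, 16 conditions of 19 families, 2000 runs per scenario:

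| q, gap | Unadjusted | Adjusted |
|---|---|---|
| 30%, 20 points | 78.5% | 80.3% |
| 30%, 30 points | 79.9% | 82.9% |
| 50%, 30 points | 80.1% | 83.2% |
| 50%, 40 points | 80.6% | 86.2% |

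Simulation error is about √(0.8·0.2/2000) = 0.9 points per entry. The pattern agrees with the formula.

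**Chance imbalance.** If state is not balanced, its share differs between the two levels of a factor with SD √[2q(1 − q)/152]. At q = 30% this is √(0.42/152) = 5.3 points, a 95% range of about ±10 points. With a 30-point gap, an estimated effect moves by up to about 10.3 × 0.30 = 3.1 points, against a 15-point target.

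**The case against.** Much of the case against narrows the point, and it stands on the following.

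- **Bias or lost power.** A reader might infer that the comparison is biased or that the trial falls short of its planned power. Neither follows. Randomisation protects the comparison. The 60% and 75% are marginal rates that already average over any mix of entry states. The unadjusted standard error, √[(0.24 + 0.1875)/152] = 5.3 points, already includes chance imbalance.
- **Visits booked beforehand.** A reader might infer that some appointments precede randomisation. No passage says so; scheduling appears among the FP's later tasks. It is only a possibility left open by the route through the behavioral health provider.
- **No contact yet.** A reader might take all of these children as not yet seen. Section 9 refers to assessment by the behavioral health clinician, so some may already have had contact. A classification that stops at a booked appointment would have no place for them.
- **The section 8 sentence.** Alone it shows one stage, not a mixture. The variation rests on the two section 9 passages.
- **Appendix A.** It appears to put referral at baseline and randomisation at baseline or month 1. Other rows in the extracted table do not line up with Tables 1 and 2, so this should carry no weight.
- **Minimisation.** The list is given as examples, and section 9 refers to a fuller account elsewhere. The variable may be in the program.

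The objection does not reach the analysis model. The 90-day logistic regression names no baseline covariate, while referrals and appointments are extracted.

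**Conclusion.** The point holds as a modest, inexpensive gain in precision. The documents allow families to enter at different steps toward the outcome, record the relevant dates, and do not use them in the 90-day model. Power moves from 80.0% to between 80.3% and 85.7% for shares of 20-50% and gaps of 10-40 points; at gaps of 20-30 points the gain is about 1-3 points. If entry state does not predict the outcome, there is no gain. The share, the gap, the two-state simplification and the 80% reference power are all assumptions. Adjustment removes no bias, because none is shown. The scheduling-time issue is conditional: it matters only if some child has a booking before randomisation.

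**What to change.** Before outcomes are examined, add to the SAP:

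1. A state at randomisation for each child, derived from EHR dates up to that day, with FP documentation for outside services: no behavioral health referral; referral placed but no appointment; appointment booked; already assessed or seen by a behavioral health clinician. Give a rule for merging sparse levels.
2. This state as a covariate in the 90-day logistic model, with the marginal risk difference reported alongside the odds ratio.
3. This state as a stratum in the time-to-receipt Cox model.
4. A rule that, if any child has an appointment booked before randomisation, the time-to-scheduling model is restricted to children without one.

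Changing the minimisation variables during enrolment is optional and not needed.

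The cost is one derived variable, a few sentences and up to three degrees of freedom. The odds ratio becomes conditional on state (2.10 in the worked case, against a marginal 3.0/1.5 = 2.00), which is why the risk difference should accompany it. Some outside referrals made before FP contact may go unrecorded, so those children could be misclassified as having none.
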